##### Continuous endpoints anticipated to have a non-normal distribution

Continuous secondary efficacy endpoints analyzed with the ITT estimand and anticipated to have a non-normal distribution (ie, TG and Lp (a)), will be analyzed using a robust regression model (ie, ROBUSTREG SAS procedure with M-estimation option) with baseline value as effect. Missing values will be addressed using a multiple imputation approach, which will be described in the SAP. The combined means will be provided with respective SE estimates and 95% CI.

Continuous secondary efficacy endpoints analyzed with the on-treatment estimand and anticipated to have a non-normal distribution will be analyzed using the same imputation and analysis models but only including on-treatment values in these models.

##### Binary endpoints

Binary secondary efficacy endpoints analyzed with the ITT estimand will be analyzed with multiple imputation approach for handling of missing values, which will be described in the SAP. Combined proportions will be provided with corresponding 95% CI.

Binary secondary efficacy endpoints analyzed with the on-treatment estimand will be analyzed using the same imputation model, but only including on-treatment values in this model.

#### **11.4.2.3 Multiplicity considerations**

Not applicable.

### 11.4.3 Analyses of safety data

The summary of safety results (see [Section 9.2.3](#)) will be presented by dose and overall. No formal inferential testing will be performed. Summaries will be descriptive in nature.

All safety analyses will be performed on the safety population, using the following common rule:

- The baseline value is defined as the last available value before first IMP injection.

The following definitions will be applied to laboratory parameters and vital signs:

- The potentially clinically significant abnormality (PCSA) values are defined as abnormal values considered medically important by the Sponsor according to predefined criteria/thresholds based on literature review and defined by the Sponsor for clinical laboratory tests and vital signs.
- The PCSA criteria will determine which patients had at least 1 PCSA during the TEAE period, taking into account all evaluations performed during the TEAE period, including unscheduled or repeated evaluations. The number of all such patients will be the numerator for the PCSA percentage.
- Treatment period: the treatment period used for quantitative analysis is defined as the time from first dose of IMP injection to the last dose of IMP injection +21 days.

#### **Adverse event definition:**

- Pre-treatment AEs are AEs that developed or worsened or became serious during the pre-treatment period.
- Treatment-emergent AEs (TEAEs) are AEs that developed or worsened or became serious during the TEAE period.
- Post-treatment AEs are AEs that developed or worsened or became serious during the POST-TREATMENT period.

#### ***Drug-induced liver injury***

Liver function tests, namely ALT, AST, ALP, and total bilirubin, are used to assess possible drug-induced liver toxicity. The proportion of patients with PCSA values at any post-baseline visit by baseline status will be displayed for each parameter. A graph of distribution of peak values of ALT versus peak values of total bilirubin will also be presented. Note that the ALT and total bilirubin values are presented on a logarithmic scale. The graph will be divided into 4 quadrants with a vertical line corresponding to 3 x ULN for ALT and a horizontal line corresponding to 2 x ULN for total bilirubin.

The incidence of liver-related AEs will be summarized. The selection of PT will be based on standardized MedDRA query (SMQ) hepatic disorder.

#### **11.4.3.1 Adverse events**

Adverse event incidence tables will present the number (n) and percentage (%) of patients experiencing an AE by SOC (sorted by internationally agreed order), HLG, HLT, and PT sorted in alphabetical order. Multiple occurrences of the same event in the same patient will be counted only once in the tables within a treatment phase. The denominator for computation of percentages is the safety population.

Adverse event incidence table will be provided for all types of TEAEs: all TEAEs, all treatment-emergent AESI and grouping of terms (prespecified grouping, eg, allergic events, LISR), all treatment-emergent SAEs, and all TEAEs leading to permanent treatment discontinuation.

#### Deaths:

The following deaths summaries will be generated:

- Number (%) of patients who died by study period (TEAE, onstudy, poststudy) summarized on the safety population.
- Death in non-treated patients.
- TEAE leading to death (death as an outcome on the AE eCRF page as reported by the Investigator) by primary SOC, HLG, HLT, and PT showing number (%) of patients sorted by internationally agreed order of SOC and alphabetic order of HLG, HLT, and PT.

#### **11.4.3.2 Laboratory data and vital signs**

The summary statistics (including mean, median, Q1, Q3, standard error, minimum, and maximum) of all laboratory variables, all vital signs parameters (raw data and changes from baseline) will be calculated for each visit, last and worst value assessed during the treatment period.

The incidence of PCSAs at any time during the TEAE period (on-treatment PCSAs) will be summarized whatever the baseline level and/or according to the following baseline categories:

- Normal/missing.
- Abnormal according to PCSA criterion or criteria.

For laboratory parameters for which PCSA criterion is not defined, similar table(s) using the normal range could be provided.

#### **11.4.4 Other endpoints**

For definitions see [Section 9.3](#).

#### **11.4.4.1 Pharmacokinetics**

Serum total alirocumab concentrations, and total and free PCSK9 concentrations will be summarized by visit using descriptive statistics by dose and overall. Serum concentration time profiles will be provided by dose and overall. Further details will be provided in the SAP.

Serum total alirocumab concentrations might be used for population PK modeling if considered necessary and the results of population PK modeling will be reported separately from the study report.

#### **11.4.4.2 Anti-alirocumab antibody assessments**

The antibody status (positive/negative) and antibody titers will be summarized by visit using descriptive statistics by dose and overall.

#### **11.4.4.3 LDL-C less than 50 mg/dL (1.30 mmol/L)**

The number and percentage of patients with 2 consecutive results, spaced out by at least 21 days, of calculated LDL-C <50 mg/dL (1.30 mmol/L), calculated LDL-C <25 mg/dL (0.65 mmol/L), calculated LDL-C <15 mg/dL (0.39 mmol/L), and the time to the first LDL-C <50 mg/dL (<25 mg/dL, <15 mg/dL respectively), will be provided by dose and overall.

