## **9 ASSESSMENT OF INVESTIGATIONAL MEDICINAL PRODUCT**

### **9.1 PRIMARY ENDPOINT**

#### **9.1.1 Primary efficacy endpoint**

Percent change in LDL-C (pre-apheresis, if applicable) from baseline to Week 12 in the intent-to-treat (ITT) population, using all LDL-C values (pre-apheresis, if applicable) regardless of adherence to treatment (ITT estimand).

The LDL-C at Week 12 will be the LDL-C level obtained within the Week 12 analysis window. All calculated and measured LDL-C values (scheduled or unscheduled, fasting or not fasting) may be used to provide a value for the primary efficacy endpoint if appropriate according to the above definition. In case both calculated and measured LDL-C are provided for the same sampling, the measured LDL-C will be considered. For patients undergoing apheresis, pre-apheresis values will be considered. The analysis window used to allocate a time point to a measurement will be defined in the statistical analysis plan (SAP).

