### **9.3.4 Pharmacodynamic variables**

The pharmacodynamic effect of alirocumab corresponding to the effect on LDL-C is described in the efficacy section (see [Section 9.1.1](#) and [Section 9.2.1](#)).

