#### **10.1.3.2 Visit 5 (Week 4)**

The following procedures/assessments will be performed:

- Compliance check of IMP and data collection on IMP administration.
- Concomitant medication recording.
- Check of stability of background LMT, including apheresis (if applicable).
- Review of diet.
- Collect AEs.
- Vital signs.
- Body weight.
- Body height.
- Fasting blood sampling for:
  - Total-C, LDL-C, HDL-C, TG, and non-HDL-C (pre-apheresis and post-apheresis, if applicable).
  - Hematology and chemistry.
  - Liver panel.
- IMP administration.

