### **Blood sample collection and overall study assessment throughout the study**

All samples for clinical laboratory (lipid and specialty lipid panels) and PK evaluations **must** be obtained immediately prior to and immediately after the LDL apheresis procedure, therefore LDL apheresis has to be administered at that visit and before study drug administration.

- Lipid panel 1 (Total-C, calculated LDL-C, HDL-C, TG, and non-HDL-C): samples should be drawn immediately prior to and immediately following the apheresis procedure.

---

 Stable apheresis is defined as 4 apheresis procedures performed during a 4 week period, approximately 1 week apart, or 4 apheresis procedures performed during an 8 week period, approximately 2 weeks apart.

*Note: Acceptable apheresis techniques are: double membrane filtration, immunoadsorption, heparin-induced LDL precipitation, direct adsorption of lipids, dextran sulfate adsorption (plasma), dextran sulfate adsorption (whole blood).*

- Alirocumab, and free and total PCSK9 levels: PK samples should be drawn immediately prior to and immediately following the apheresis procedure.
- Specialty lipid panel (lipid panel 2: Apo B, Apo A-1, and Lp (a)): samples should be drawn immediately prior to apheresis (where applicable).
- ADA assessment: samples should be drawn prior to apheresis (where applicable).

Study assessments such as vital signs, BP etc, have to be done before apheresis, and alirocumab is to be administered after apheresis.

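### Does Section 11.4.4.3 need to name the apheresis sample that counts for LDL-C below 50, 25 and 15 mg/dL?

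*Protocol*

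**What the plan says.** Section 11.4.4.3 of the protocol defines two outputs for calculated LDL-C below 50, 25 and 15 mg/dL. The first is "The number and percentage of patients with 2 consecutive results, spaced out by at least 21 days", below each threshold. The second is the time to the first value below each threshold: "the time to the first LDL-C <50 mg/dL (<25 mg/dL, <15 mg/dL respectively), will be provided by dose and overall". Neither names an apheresis sample.

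For patients on apheresis, Appendix A asks that lipid panel 1 "samples should be drawn immediately prior to and immediately following the apheresis procedure". The visit lists agree; Section 10.1.3.2 (Week 4), for example, asks for "Total-C, LDL-C, HDL-C, TG, and non-HDL-C (pre-apheresis and post-apheresis, if applicable)", and the same line stands at Day 1 and Weeks 12, 24 and 48.

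Elsewhere the protocol does choose a sample. Exclusion criterion E 02 and four of the five secondary efficacy endpoints in Section 9.2.1 carry the pre-apheresis qualifier. Section 9.1.1, on the primary endpoint, says: "For patients undergoing apheresis, pre-apheresis values will be considered". Section 11.4.4 refers to Section 9.3 for definitions, and Section 9.3.4 adds: "The pharmacodynamic effect of alirocumab corresponding to the effect on LDL-C is described in the efficacy section", citing Sections 9.1.1 and 9.2.1.

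**The concern.** Section 11.4.4.3 fixes the thresholds, the use of calculated LDL-C, the repeat requirement and the spacing, yet is silent on the one choice that separates a drug effect from a mechanical one. A patient on apheresis has two LDL-C values on the same visit day, and the second is lowered by the procedure itself. If that second value counts, a patient who was never below 50 mg/dL before apheresis could appear in the low LDL-C table.

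The start of observation also looked open. On Day 1, "LDL apheresis has to be administered at that visit and before study drug administration", so a post-apheresis value exists before any alirocumab has been given.

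At stake is the reading of a safety-relevant table in a small trial: one patient is 1/18 = 5.6% of the planned enrolment. Low LDL-C is also a topic for the data monitoring committee (Section 6.4.2).

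**Working it through.** The protocol gives no figure for this table, so there is none to reproduce. The check has three parts.

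**1. When could the choice of sample matter?**

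Inputs:
- Reduction by apheresis, r = 30% to 75% (Appendix A, Introduction), read here as the fall across one procedure.
- Entry limit of 130 mg/dL, pre-apheresis (E 02).
- Drug effect d = 24% or 51%. These are mean reductions that Section 4 cites for another PCSK9 inhibitor; using them here is an assumption, and individual patients vary.

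A post-apheresis value is below threshold T when the pre-apheresis value is below T/(1 − r):

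| T (mg/dL) | r = 30% | r = 75% |
|---|---|---|
| 50 | 50/0.70 = 71.4 | 50/0.25 = 200 |
| 25 | 25/0.70 = 35.7 | 25/0.25 = 100 |
| 15 | 15/0.70 = 21.4 | 15/0.25 = 60 |

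The matching baseline limit is T/[(1 − r)(1 − d)]. For T = 50:

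| r | d = 0 | d = 24% | d = 51% |
|---|---|---|---|
| 50% | 50/0.50 = 100 | 50/(0.50 × 0.76) = 131.6 | 50/(0.50 × 0.49) = 204.1 |
| 75% | 50/0.25 = 200 | 50/(0.25 × 0.76) = 263.2 | 50/(0.25 × 0.49) = 408.2 |

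Examples:
- Baseline 130, d = 0, r = 75%: 130 × 0.25 = 32.5, below 50.
- Baseline 130, d = 24%: 130 × 0.76 = 98.8 before apheresis; 49.4 after 50% removal and 24.7 after 75%.
- Baseline 300, d = 24%, r = 75%: 300 × 0.76 × 0.25 = 57, not below 50. Removal of 1 − 50/228 = 78.1% would be needed.
- Baseline 500, d = 51%, r = 75%: 500 × 0.49 × 0.25 = 61.25, not below 50.
- T = 15, d = 51%, r = 75%: the baseline limit is 15/(0.25 × 0.49) = 122.4, under the 130 entry limit, so no eligible baseline reaches it under these assumptions.

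The choice can therefore matter only for apheresis patients with comparatively low LDL-C. Section 4 expects a very high baseline despite optimal treatment, and the Clinical Trial Summary calls values below 50 mg/dL unlikely in this population.

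**2. Which output is exposed?**

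The time to first value is exposed, because a single result suffices. The repeat count is largely protected. In strict time order, neighbouring values are either a same-day pair, which fails the 21-day spacing, or a post-apheresis value followed by the next visit's pre-apheresis value, which then has to be low itself. Two post-apheresis values pair up only if the pre-apheresis value between them is ignored.

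**3. What would an analyst do with the text?**

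- E 02, Section 9.1.1 and four of five endpoints in Section 9.2.1 select the pre-apheresis value. No eligibility or efficacy rule for LDL-C selects the post-apheresis one.
- The references run from Section 11.4.4 to 9.3, and from 9.3.4 to 9.1.1, where the pre-apheresis rule stands. The route is indirect, but it ends in one place.
- Section 11.4.3 takes the last value before the first injection as baseline and starts the treatment period for quantitative analysis at that injection. Section 10.6.3 ties the 50 mg/dL threshold to the treatment period. A Day 1 value drawn before the injection is thus pre-treatment, and counting it as an event on alirocumab would be a strained reading.

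**The case for a change.** The best case for a change is that Section 11.4.4.3 does not hand its derivation to the SAP. Section 9.1.1 defers its analysis windows and Section 11.4.4.1 defers further pharmacokinetic detail, whereas this paragraph writes out its own rules and leaves one out. The pre-apheresis sentence belongs to the primary endpoint, Section 9.3 contains no definition of the low LDL-C analysis, and the common safety rules in Section 11.4.3 choose no apheresis sample. A few words would settle the matter at no cost in data.

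Most of that is correct: the sample is not named, and no rule formally extends the pre-apheresis choice to this table. It shows an unfilled detail, not an error. Nothing in the paragraph is false or conflicts with another section. One secondary endpoint, the absolute change in LDL-C, lacks the qualifier beside four that carry it, which points to drafting shorthand more than to a different intended sample. The protocol text alone does not show that post-apheresis values would be used.

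Sections 10.6.3 and 6.4.2 use the same threshold without naming a sample. They concern patient management and safety oversight, and no view is taken here on which sample should apply there.

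**Conclusion.** No change to the plan is called for. The gap is real but is of the kind a protocol commonly leaves to the SAP, and an analyst following the protocol's other LDL-C rules would use the pre-apheresis value. If a post-apheresis value were used instead, the time to first LDL-C below 50 mg/dL could be affected for apheresis patients with pre-apheresis values under 71 to 200 mg/dL, depending on removal. Each such patient would be 5.6% of 18. The number on apheresis is not stated and may be zero. The table is descriptive, and the primary result and all inferential results are untouched.

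This rests on reading the 30% to 75% range as the fall across one procedure, and on borrowing mean drug effects of 24% and 51% from another PCSK9 inhibitor. The SAP was not available to this review, so whether it names the sample is not known.

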#### **11.4.4.4 Creatine phosphokinase-MB and cardiac troponin**

Creatine phosphokinase-MB and cardiac troponin (value and percent change from baseline) at Week 12 will be summarized on the safety population using number of available data, mean, SD, median, Q1, Q3, minimum, and maximum for each dose and overall. In addition, the incidence of PCSA at any time during the TEAE period will be summarized by dose and overall using descriptive statistics.

### **11.5 INTERIM ANALYSIS**

No interim analysis is planned (see [Section 6.3](#)).

## **12 ETHICAL AND REGULATORY CONSIDERATIONS**

### **12.1 ETHICAL AND REGULATORY STANDARDS**

This clinical trial will be conducted by the Sponsor, the Investigator, and delegated Investigator staff and Subinvestigator, in accordance with consensus ethics principles derived from international ethics guidelines, including the Declaration of Helsinki, and the ICH guidelines for Good Clinical Practice (GCP), all applicable laws, rules, and regulations.

This clinical trial will be recorded in a free, publicly accessible, internet-based registry, no later than 21 days after the first patient enrollment, in compliance with applicable regulatory requirements and with sanofi public disclosure commitments.

### **12.2 INFORMED CONSENT**

The Investigator (according to applicable regulatory requirements), or a person designated by the Investigator, should fully inform the patient (and the parent[s] or guardian[s]) of all pertinent aspects of the clinical trial including the written information given approval/favorable opinion by the ethics committee (IRB/IEC). All participants should be informed to the fullest extent possible about the study in language and terms they are able to understand.

Prior to a patient's participation in the clinical trial, the informed consent form should be signed, name filled in, and personally dated by the patient's parent(s) or by the patient's legally acceptable representative, and by the person who conducted the informed consent discussion. Local law must be observed in deciding whether 1 or both parents/guardians consent is required. If only 1 parent or guardian signs the consent form, the Investigator must document the reason for only 1 parent or guardian's signature.

In addition, participants will assent as detailed below or will follow the IRB/IEC approved standard practice for pediatric participants at each participating center (age of assent to be determined by the IRBs/IECs or be consistent with the local requirements):

Participants who can read the assent form will do so before writing their name and signing and dating the form.

Participants who can write but cannot read will have the assent form read to them before writing their name on the form.

Participants who can understand but who can neither write nor read will have the assent form read to them in presence of an impartial witness, who will sign and date the assent form to confirm that assent was given.

The informed consent form and the assent form used by the Investigator for obtaining the patient's informed consent must be reviewed and approved by the Sponsor prior to submission to the appropriate ethics committee (IRB/IEC) for approval/favorable opinion.

In relation with the population of patients exposed in the trial, ie, pediatric/minor patients, the IRB/IEC should ensure proper advice from specialist with pediatrics expertise (competent in the area of clinical, ethical, and psychosocial problems in the field of pediatrics) according to national regulations. This should be documented.

Prior to collection of blood for genotyping for hoFH and/or for use of previous documented genotyping, the optional informed consent section within the main informed consent form (written) should be signed, name filled in, and personally dated by the patient or by the subject's legally acceptable representative, and by the person who conducted the informed consent discussion. A copy of the signed and dated written optional informed consent form will be provided to the subject.

The informed consent form and the optional genotyping informed consent obtained by the Investigator for obtaining the patient's informed consent must be reviewed and approved by the Sponsor prior to submission to the appropriate ethics committee (IRB/IEC) for approval/favorable opinion.

A copy of the signed and dated written informed consent form(s) will be provided to the patient or legal representative.

### **12.3 HEALTH AUTHORITIES AND INSTITUTIONAL REVIEW BOARD/INDEPENDENT ETHICS COMMITTEE (IRB/IEC)**

As required by local regulation, the Investigator or the Sponsor must submit this clinical trial protocol to the health authorities (competent regulatory authority) and the appropriate IRB/IEC, and is required to forward to the respective other party a copy of the written and dated approval/favorable opinion signed by the chairman with IRB/IEC composition.

The clinical trial (study number, clinical trial protocol title and version number), the documents reviewed (clinical trial protocol, informed consent form, Investigator's Brochure with any addenda or labeling documents [summary of product characteristics, package insert, etc], Investigator's curriculum vitae), and the date of the review should be clearly stated on the written (IRB/IEC) approval/favorable opinion.

The IMP will not be released at the study site and the Investigator will not start the study before the written and dated approval/favorable opinion is received by the Investigator and the Sponsor.

During the clinical trial, any amendment or modification to the clinical trial protocol should be submitted to the health authorities (competent regulatory authority), as required by local regulation, in addition to the IRB/IEC before implementation, unless the change is necessary to eliminate an immediate hazard to the patients, in which case the health authorities (competent regulatory authority) and the IRB/IEC should be informed as soon as possible. They should also be informed of any event likely to affect the safety of patients or the continued conduct of the clinical trial, in particular any change in safety. All updates to the Investigator's Brochure will be sent to the IRB/IEC and to health authorities (competent regulatory authority), as required by local regulation.

A progress report is sent to the IRB/IEC at least annually and a summary of the clinical trial's outcome at the end of the clinical trial.

